9.1 Definition of baseline and change from baseline

In general, the last non-missing measurement prior to the first study drug administration will be used as the baseline measurement.

If an assessment that is planned to be performed before treatment per protocol is performed on the same day as the start of treatment, respectively, but the assessment time is not available, it will be assumed that it was performed prior and will be considered as baseline.

If a scheduled pre-dose measurement actually occurred post-dose, then the corresponding measurement will be analyzed similar to an unscheduled post-dose measurement.

Absolute and percent changes from baseline are defined as

$$\text{absolute change} = \text{post baseline value} - \text{baseline value}$$

$$\text{percent change} = 100 * (\text{post baseline value} - \text{baseline value}) / \text{baseline value}$$

9.2 Definition of Duration and 'time since' Variables

If not otherwise specified, duration will be calculated by the difference of start and stop date + 1 (e.g. survival time (days) = date of death – date of first study drug administration + 1).

The time since an event (e.g. time since first diagnosis) will be calculated as reference date minus date of event.

9.3 Conversion factors

The following conversion factors will be used to convert days into months or years: 1 month = 30.4375 days, 1 year = 365.25 days.

9.4 Definition of On-treatment Period

The on-treatment period is defined as the time from first dose of study intervention to 30 days after end of study intervention, or the cut-off date, whichever occurs first.

9.5 Imputation of missing data

Unless otherwise specified all data will be evaluated as observed, and no imputation method for missing values will be used.

In all participant data listings, imputed values will be presented and imputed information will be flagged, if imputation was done.

Missing statistics, e.g. when they cannot be calculated, should be presented as “nd”.

Where tables are presented over different time points, the total of missing and non-missing observations at each time-point should reflect the population still in the trial at that time. This does not apply when imputations are made beyond trial withdrawal. For example, if a participant is still in the trial at the time-point but with missing data, they should be counted in the number of missing observations.

The following table for imputation rules will be considered:

Adverse events	
Incomplete AE-related dates will be imputed as follows:
 
• If the onset date is missing completely or missing partially – but the onset month and year, or year, are equal to that of the study treatment start – then the onset date will be replaced by the minimum of the start of study treatment and the AE resolution date.• In all other cases, the missing onset day or month will be replaced by 1.• Incomplete stop dates will be replaced by the last day of the month (if day is missing only), if not resulting in a date later than the date of participant's death. In the latter case, the date of death will be used to impute the incomplete stop date.
----------------	---

	
 • In all other cases the incomplete stop date will not be imputed. If the stop date of an AE is after the date of cut-off, the outcome of the AE is ongoing at cut-off. • Further information after cut-off (such as fatal outcome) might be taken from the Safety database and reported separately.
Previous and concomitant medication	For identification of previous or concomitant medications/procedures, no formal imputation will be performed on missing or incomplete dates. Rules presented in Table 2 will be used to define if a medication/procedure is considered as a previous, concomitant or both previous and concomitant medication/procedure.

Table 1 Imputation rules for medication/procedure end dates

End date of medication/procedure			imputation rule
Day	Month	Year	
UNK	UNK	UNK	After treatment start (ongoing)
UNK	UNK	< Treatment start (year)	Before treatment start
UNK	UNK	\geq Treatment start (year)	After treatment start
UNK	< Treatment start (month and year)		Before treatment start
UNK	\geq Treatment start (month and year)		After treatment start
< Treatment start (complete date)			Before treatment start
\geq Treatment start (complete date)			After treatment start

UNK = Unknown

Table 2 Rules to define previous and/or concomitant medication

Start date of medication/procedure			imputatio rule (see Table 1)	Medication/procedure
Day	Month	Year		
UNK	UNK	UNK	Before treatment start	Previous
UNK	UNK	UNK	After treatment start	Previous and concomitant
UNK	UNK	\leq Treatment start (year)	Before treatment start	Previous
UNK	UNK	\leq Treatment start (year)	After treatment start	Previous and concomitant

Start date of medication/procedure			imputation rule (see Table 1)	Medication/procedure
Day	Month	Year		
UNK	UNK	> Treatment start (year) and <= Treatment end + 30 days (year)	After treatment start	Concomitant
UNK		<= Treatment start (month and year)	Before treatment start	Previous
UNK		<= Treatment start (month and year)	After treatment start	Previous and concomitant
UNK		> Treatment start (month and year) and <= Treatment end + 30 days (month and year)	After treatment start	Concomitant
<= Treatment start (date)			Before treatment start	Previous
<= Treatment start (date)			After treatment start	Previous and concomitant
> Treatment start (date) and <= Treatment end + 30 days (date)			After treatment start	Concomitant

UNK = Unknown

Death date Note: For participants who died and for whom no complete death date is available usually the death date is not imputed. Just for survival analyses imputation rules are applied, in death listings non-imputed data will be presented.	For the purpose of survival analyses partially missing death dates will be imputed as follows: If only the day is missing, the death date will be imputed to the maximum of the (non-imputed) day after the date of last contact and the 15th day of the month. Otherwise it will not be imputed.
--	---

9.6 Study Day / Study Treatment Day definition

Treatment day is defined relative to the date of first study drug administration (M3258). Treatment Day 1 is treatment start date of first administration of the study drug; the day before is defined as Treatment Day -1 (no Treatment Day 0 is defined).

10**Study Participants**

The subsections in this section include specifications for reporting participant disposition and study intervention/study discontinuations. Additionally, procedures for reporting protocol deviations are provided.

10.1**Disposition of Participants and Discontinuations**

A table will display the following (per regimen and dose level and overall):

- Number of participants in each analysis population (SCR, SAF, DLT, PK, Pd)
- Number of participants who discontinued from the study prior to treatment overall and grouped by the main reason (participants did not meet eligibility criteria, withdrew consent, other)

This table will be produced twice if there are participants with differing planned dose and actual dose, one by planned dose (including SCR, SAF, Pd, PK) and one by actual dose (including SCR, SAF, DLT, PK).

This table will additionally be displayed by site.

Another table of disposition will provide the following, among participants in SAF:

- Number and percentage of participants still in trial
- Number and percentage of participants withdrawn from trial
- Number of participants by reason for withdrawal

Additionally a listing will display all discontinued patients including planned regimen and dose, the reason for discontinuation from treatment and reason for discontinuation from study and treatment start and end date.

10.2**Protocol Deviations / Exclusion from Analysis Population****10.2.1****Important Protocol Deviations**

Important protocol deviations (IPDs) are protocol deviations that might significantly affect the completeness, accuracy, and/or reliability of the study data or that might significantly affect a participant's rights, safety, or well-being.

The IPDs will be identified for all participants by either site monitoring, medical review processes or programming and confirmed prior to or at the Data Review Meeting at the latest.

All important protocol deviations are documented in SDTM datasets whether identified through site monitoring, medical review or programming.

A full list of potential protocol deviations including definition and categorization is maintained by Covance in the "Study Specific Protocol Deviation List" attached to the Protocol Deviation Management Plan.

A frequency table for important, separated for such pre-/post inclusion deviations, as well as a listing (by participant) of important protocol deviations, will be provided based on the Safety analysis set.

Referring to FDA, a listing of all participants affected by the COVID-19 related study disruption will be produced by unique subject number identifier and by investigational site, and a description of how the individual's participation was altered.

The protocol deviations are detailed in the document MS201814-0010 Protocol Deviation Listing_14Nov2019_v1.0.xlsx or an updated version.

10.2.2 Reasons Leading to the Exclusion from an Analysis Population

A listing of reasons for exclusion from DLT analysis population will be provided.

Additionally a listing of subjects excluded from analysis sets (DLT, SAF, PK,Pd) with reason for exclusion will be provided (for section 9.2.3).

Of note, participants who did not receive at least 80% of the planned dose are excluded from the DLT analysis set unless they can be considered in another dose level as described in [Sections 8](#) and [10.2.1](#).

11 Demographics and Other Baseline Characteristics

If not stated otherwise, the following analyses will be performed based on the SAF, by regimen and dose, and overall.

11.1 Demographics

Demographic characteristics and physical measurements will be summarized descriptively using the following information from the Screening/Cycle 1 Day 1 eCRF pages.

The following demographic characteristics will be included:

Sex: Male, Female

Race: White, Black or African American, Asian, American Indian or Alaska Native, Native Hawaiian or Other Pacific Islander, Not collected at this site, Other

Ethnic origin: Hispanic or Latino/Not Hispanic or Latino

Age (years)

Age categories :< 65 years, ≥ 65 years

Pooled Region: North America, Europe, Asia, Rest of the World)

Geographic Region: North America, Latin America, Western Europe, Eastern Europe, Middle East, Australia, Asia

Weight (kg)

BMI (kg/m²) at Baseline

Eastern Cooperative Oncology Group (ECOG) Performance status (0,1,2,3,4)

Specifications for computation:

- Age [years]: (date of given informed consent – 01JANYYYY + 1) / 365.25, where YYYY is the year of birth as collected in eCRF. The integer part of the calculated age will be used for reporting purposes.
- BMI [kg/m²] = $\frac{\text{weight [kg]}}{\text{height [cm]}^2} \times 10000$
- Site codes will be used for the determination of the participant's geographic region.

Additionally demographic data will be presented in a listing.

11.2 Medical History

The medical history will be summarized from the "Medical History" eCRF page, using the most recent MedDRA version at time of database lock, preferred term as event category and system organ class (SOC) body term as Body System category. Each participant will be counted only once within each PT or SOC.

Medical history will be displayed in terms of frequency tables: ordered by primary SOC and PT in alphabetical order.

Additionally medical history data will be presented in a listing.

11.3 Other Baseline Characteristics

Information on disease characteristics collected at baseline will be summarized. Summary statistics will be presented for (as applicable)

- Prior transplant:
 - Stem cell transplant (Yes, No)
 - Stem cell type (Bone marrow, Peripheral blood stem cell)
 - Single or Tandem transplant
 - Type of transplant (Autologous Stem Cell Transplant, Allogenic Stem Cell Transplant)
 - Chemotherapy (Yes, No)
 - Total Body Irradiation (Yes, No)
- History of disease under study:
 - Time since initial diagnosis
 - Type of myeloma at diagnosis (IgG, IgM, IgA, IgD, IgE)
 - Light chain of myeloma at diagnosis (Lambda, Kappa)
 - ISS stage at diagnosis (I, II, III)
- Disease characteristics at study entry:
 - Type of myeloma at (IgG, IgM, IgA, IgD, IgE)
 - Light chain of myeloma (Lambda, Kappa)
 - ISS stage (I, II, III)
- Presence of bone lesions at Cycle 1 Day 1 (based on page “Osteolytic bone lesion assessment”)

All these other baseline characteristics along with substance usage (Drug, alcohol, nicotine and caffeine consumption) and family history of premature cardiovascular disease will be listed for primary analysis

Baseline characteristics with respect to vital signs and laboratory (including hematology/biochemistry) will be part of Section **Error! Reference source not found.** (Safety E valuation).

11.4 Prior Anti-cancer Therapy

The prior anti-cancer therapies are collected under the “Prior Anti-Cancer Drug Therapies Details”, “Prior Anti-Cancer Radiotherapy Details” and “Prior Anti-Cancer Surgeries Details” eCRF pages.

The number and percentage of participants in each of the following anti-cancer therapy categories will be tabulated:

- Participants with at least one prior anti-cancer drug therapy
- Participants with at least one prior anti-cancer radiotherapy
- Participants with at least one prior anti-cancer surgery

This table will also tabulate the number of prior anticancer therapies, prior anticancer drug therapies, prior anti-cancer radiotherapies and number of prior anti-cancer surgeries.

The listing of prior anti-cancer treatments and procedures will also be provided as follows. These will include the participant identification number, and all the relevant collected data-fields on the corresponding eCRF pages (including if chemotherapy was associated to a stem cell transplant).

- Listing of prior anti-cancer drug therapies
- Listing of prior anti-cancer radiotherapy
- Listing of prior anti-cancer surgeries

12

Previous or concomitant medications/interventions

The following analyses will be performed based on the SAF analysis set, by regimen and by dose (in increasing order) and summarized

Concomitant treatments are medications, other than study treatment, which are taken by participants any time during the on-treatment period, see section 9.4.

Previous medications are medications, other than study treatment and pre-medications for study treatments, which started before first administration of study treatments.

A medication may be classified as both concomitant and previous. The respective flags will be derived based on start and end date.

Concomitant and previous treatment each will be summarized by number and percentage of participants from the “Relevant Previous medications” and “Concomitant medications” eCRF. ATC-2nd level and preferred term will be tabulated as given from the WHO-DD dictionary most current version. If any previous or concomitant medication is classified into multiple ATC classes, the medication will be summarized separately under each of these ATC classes. The summary tables will be sorted by decreasing frequency of drug class and decreasing frequency of drug name in a given drug class. In case of equal frequency regarding drug class (respectively drug name), alphabetical order will be used. In case any specific medication does not have an ATC classification level 2 coded term, it will be summarized under “Unavailable ATC classification”

category. Each participant will only be counted once, even if he/she received the same medication at different times.

All concomitant treatments, previous medications and **concomitant procedures**, which were undertaken during the on-treatment period will be listed. Concomitant procedures according to the CRF page "Concomitant Procedures".

13 Study intervention Compliance and Exposure

The following analyses will be performed based on the SAF analysis set, by regimen and dose (in increasing order) and summarized

All dosing calculations and summaries will be based on CRF "M3258 Administration Details", , in particular for first study drug administration.

The date of last study drug administration will be defined as the last date in the "M3258 Administration Details", with dose>0.

No imputation of missing start dates of study treatments will be done.

In case the last date of study drug is incomplete the date of last study drug administration will be taken from the End of Treatment page.

Interruption of treatment will be identified in the "M3258 Administration Details", with no dose.

Each study drug (M3258 and dexamethasone) will be analyzed separately.

A dose is regarded to be administered, if the actual dose received ("Dose per administration") is > 0

For the end of dose escalation analysis, the summary of treatment exposure will include the following information:

- Exposure duration (in weeks) as defined by (date of last dose of study drug–date of first dose of study drug +1)/7
- Number of dosing days (in days) as defined by (date of last dose of study drug–date of first dose of study drug–sum of days with dose interruption +1)
- Total number of cycles received at least 80% of planned dose as defined sum of cycles with received dose \geq 80% of planned dose
- Number and percentage of participants with at least one dose reduction will be presented.

A listing will be provided for all administrations of participants (date and dose of administration) including planned regimen and dose.

14**Efficacy Analyses**

The following analyses will be performed based on the SAF analysis set, by regimen and dose (in increasing order) and summarized. In case the received cumulative dose of a participant is higher than planned cumulative dose the participant will not be considered in efficacy analyses.

14.1**Overall Response**

Overall response (OR) will be assessed based on reported overall responses at different evaluation time points from the treatment start date in accordance to IMWG response criteria, taking requirements for confirmation into account as detailed below.

OR is defined as a confirmed (2 consecutive assessments made at any time before the institution of any new therapy) Best Overall Response of sCR, CR, VGPR, or PR according to IMWG response criteria.

Participants will be considered evaluable for response in the analysis set if they have at least two on-treatment assessment of IMWG response criteria other than Not Evaluable (NE).

Except for participants who have at least one on-treatment assessment of IMWG response criteria and who receive anti-tumor treatments other than the study treatment, die, progress or withdraw for any reason prior to reaching confirmed sCR, CR, VGPR or PR. These will be considered as non-responders in the assessment of OR.

Each evaluable participant will have an objective response status (0: 'no OR'; 1: 'OR') The participants who are not evaluable will be considered Not Evaluable (NE).

OR rate (ORR) is the proportion of participants with OR in the participants evaluable for response in the analysis set.

The ORR by regimen and dose and in summary will be calculated along with the two-sided 95% CI using the Clopper-Pearson method (exact CI for a binomial proportion as computed by default by the SAS FREQ procedure using the EXACT option).

A table will display the number and percentage of participants evaluable for response, the participants with overall response, including the confirmed IMWG response criteria

Moreover, this descriptive table will include each category of Best Overall Response (sCR, CR, VGPR, PR, MR, SD, PD, NE) according the confirmed and not confirmed IMWG response criteria.

A listing will be also be provided with all IMWG assessments, specifying also the indicators for progressive disease and indicators for clinical relapse, as collected in the CRF.

14.2**Duration of treatment**

A duration of treatment plot by actual time grouped by dose level will be plotted. The plot will be in increasing order of drug intensity (10mg QD at the bottom, the 10mg BIW in the middle and the 20mg BIW at the top) Tumor assessments will be displayed with outcome (e.g. PD or SD)

Molecular information on cytogenetic abnormality (if available) will be specified at the end of each bar.

An arrow at the end of the bar plot will identify the patient with treatment ongoing at the data cut off.

The sCR and CR will be grouped and NE not presented.

14.3**M-protein and FLC**

Serum and urine M-protein (in g/dL and mg/24h respectively) and FLC ratio and FLC values (kappa and lambda) will be listed for all cycles. Changes from baseline will be added to the listing

In all further analysis the affected light chain only will be considered (as per “type of light chain” from eCRF, or if information not available, light chain type with $> 10\text{mg/L} = 1\text{mg/dL}$ at baseline)

The values for serum and urine mprotein, FLC ratio and affected light chain will be summarized using descriptive statistics of relative changes from baseline for each cycle. End of treatment visit will be summarized separately.

Figures

The following graphics will be plotted:

- A waterfall plot depicting the best % change from baseline between serum M-protein, urine M-protein and affected free light chain. Only the best change from the three different biomarkers will be depicted. Displays of serum M-protein will be identified by a circle, the urine M-protein by a triangle, the affected free light chain by a cross. The bar plot will be filled with different color depending of the dose level. If available, filled boxes below the waterfall plot will signify whether a high cytogenetic abnormality (del(17p), t (4;14) t (14;16)) was detected in the patient. Subject ID will be available below the bars.
- A spider plot by actual time for change from baseline for serum M-protein. The line will be drawn with different line types depending of the dose level. Color will be used to separate individual participants. The % change exceeding 100% will be identified with gray squares for actual values by treatment day
- A spider plot by actual time for change from baseline for affected free light chain. The line will be drawn with different line types depending of the dose level. Color will be used to separate

individual participants. The % change exceeding 100% will be identified with gray squares for actual values by treatment day

15 Safety Analyses

The subsections in this section include specifications for summarizing safety endpoints that are common across clinical studies such as adverse events, laboratory tests and vital signs.

The primary endpoint during dose escalation is the occurrence of DLTs, AEs and other safety related measurements.

The analysis population for the DLT analysis will be the DLT analysis set, for all other safety analyses it will be the SAF analysis set.

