Screening will be performed within 28 days prior to Day 1 of M3258 administration. The Screening period should start before the SMC decision to enroll participants to the next study intervention cohort. Treatment of the participants screened for future dosing cohorts will only start after the SMC decision to proceed to the next dosing cohort. If there are no clinically significant findings at Screening and the participant meets all the protocol-defined inclusion criteria and none of the exclusion criteria, the participant will be considered as eligible and will be enrolled into the study. Participants who fail to meet the protocol-specified criteria or who withdraw their consent will be considered Screening Failures.

Treatment Period

During dose escalation (Part A), M3258 will be administered QD as a single agent in 28-day cycles. In the expansion cohort (Part B), M3258 will be administered in combination with dexamethasone at a cumulative dose of 40mg/week. The treatment period will begin at the first dose of M3258 in Day 1 Cycle 1. Participants who tolerate M3258 without significant clinically relevant toxicities may continue to receive their assigned dose if there is no evidence of disease progression.

If QD treatment is not tolerated at a dose level showing efficacy and/or Pd marker signals, the following options will be considered by the SMC based on available data:

- QD dosing at doses below the non-tolerated dose (down to 1mg) in 28-day cycles (based on SMC recommendation)

OR

- Twice-per-week dosing on Days 1, 4, 8, 11, 15, 18, 22 and 25 in 28-day cycles

In addition, if a consistent reduction in platelet counts to thrombocytopenia \geq Grade 3 is observed during a 28-day dosing regimen without recovery to baseline or \leq Grade 2 by the end of the cycle, the SMC can consider a drug holiday of at least 7 days in the proposed regimen below. Similar to pan-proteasome inhibitors, a transient effect on megakaryocyte function, possibly related to platelet budding needs to be considered rather than a megakaryocyte cytotoxicity (Lonial et al, 2005). A predicted time for recovery of platelet counts from nadir to baseline values has been described to be around 7 days (Lonial et al, 2005). Thus, a drug holiday (intermittent) of at least 7 to 10 days is included in the proposed regimen below which consequently changes the cycle length to 21 days.

- QD dosing on Days 1 to 14, no dosing on Days 15 to 21, in 21-day cycles

OR

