6.4 Study Intervention Compliance

In this study, participants will receive study intervention at the investigational site on visit days. Trained medical staff will monitor and/or perform the on-site study intervention administration. Participants will be instructed by the Investigator/designee regarding off-site self-administration of M3258, and compliance checks performed at all study visits. The information of each study intervention administration (date and dose of study intervention) will be recorded in the participant notes and electronic Case Report Form (eCRF). On days preceding PK, sampling time of drug intake will also be recorded. The Investigator will ensure that the information entered into the eCRF regarding drug administration is accurate for each participant. Any reason for noncompliance should be documented. In the situation where participants discontinue study intervention for more than 5 days per cycle, or if ≥ 6 consecutive planned doses of M3258 are missed for reasons other than toxicity unless, upon consultation with the Sponsor and the review of safety and efficacy, continuation is agreed upon (Sections 7.1 and 8.4).

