- 1) All DLT data from the dose escalation will be included in a two-parameter logistic regression model (intercept and slope over log of the scaled dose, no prior; if the model does not converge, it will be reported as not calculable; the program code for this analysis can be found in the TLF shells).
- 2) The dose with targeted toxicity probability of 25% will be identified.
- 3) The next lower tested dose will be selected.

The two-sided confidence interval for the DLT probability will be provided.

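### The SAP formula for number of dosing days, read plainly, counts the planned off-days of twice-weekly dosing: 25 instead of 8 after one full 28-day cycle

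*SAP*

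**What the plan says.** SAP Section 13 (Study intervention Compliance and Exposure) includes a row for "Number of dosing days (in days) as defined by (date of last dose of study drug" minus the date of first dose, minus the sum of days with dose interruption, plus 1). Planned off-days are not mentioned.

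The same section says how interruptions are found: "Interruption of treatment will be identified in the" M3258 Administration Details page, as entries with no dose. It also defines an administered dose: "A dose is regarded to be administered, if the actual dose received" is above zero. It plans a participant-level listing: "A listing will be provided for all administrations of participants (date and dose of administration) including planned regimen and dose".

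Protocol Section 6.4 describes what sites record: "The information of each study intervention administration (date and dose of study intervention) will be recorded" in the participant notes and the eCRF.

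Protocol Section 4.1 allows a switch from daily dosing to "Twice-per-week dosing on Days 1, 4, 8, 11, 15, 18, 22 and 25 in 28-day cycles", and also gives a 21-day twice-weekly schedule on Days 1, 4, 8 and 11. SAP Section 14.2 orders its treatment-duration plot by the cohorts "10mg QD at the bottom, the 10mg BIW in the middle and the 20mg BIW at the top", so two of the three named cohorts are twice weekly. Section 14.2 does not state their cycle length.

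**The concern.** The formula takes the span from first to last dose and removes only interruptions. It counts dosing days correctly if drug is due on every day of the span, as under continuous daily dosing. Under twice-weekly dosing most days of the span are days on which no drug is due.

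The plain meaning of interruption does not cover those days. SAP Section 15.2.2 groups interruption with discontinuation and dose reduction as something an adverse event leads to, and Protocol Section 6.6 (Table 13) uses it for toxicity management. Protocol Section 4.1 describes planned gaps as days without dosing or as a drug holiday. An off-day also involves no administration, so Protocol Section 6.4 gives sites no reason to record one.

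At stake is whether a row labelled as dosing days means what it says. With no interruption it is simply the exposure duration in days, so it adds nothing to the exposure-duration row above it. The overall summary column would then combine true counts from the daily cohort with inflated counts from the twice-weekly cohorts.

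**Working it through.** The documents state no dosing-day figure, so there is none to reproduce. The check is date arithmetic on the protocol's schedules.

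**Inputs**
- Formula (SAP Section 13): last dose day − first dose day − interruption days + 1.
- 28-day twice-weekly schedule (Protocol Section 4.1): 8 doses per cycle, the first on Day 1 and the last on Day 25.
- 28-day daily schedule: 28 doses per cycle, the last on Day 28.
- Full compliance, no interruption.

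**Daily dosing, one cycle.** Formula: 28 − 1 − 0 + 1 = 28. True count: 28. The formula works here.

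**Twice-weekly dosing, one cycle.** Formula: 25 − 1 − 0 + 1 = 25. True count: 8. The difference of 25 − 8 = 17 is exactly the planned off-days between first and last dose. The ratio is 25/8 = 3.1.

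**Comparison of regimens after one cycle.** The row shows twice-weekly dosing at 25/28 = 89% of the daily count. The true figure is 8/28 = 29%.

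**Longer treatment (illustrative; the documents do not show how long participants stayed on treatment).** The last dose of cycle n falls on day 28(n − 1) + 25, and the true count is 8n.
- Two cycles: 53 against 16 (3.3 times).
- Six cycles: 165 against 48 (3.4 times).

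**21-day twice-weekly schedule, if that was the one used.** The last dose of cycle n falls on day 21(n − 1) + 11, and the true count is 4n.
- One cycle: 11 against 4 (2.8 times).
- Six cycles: 116 against 24 (4.8 times).

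**No fixed correction factor.** Suppose the Day 15 and Day 18 doses of one 28-day cycle are missed, leaving 8 − 2 = 6 true dosing days.
- Entered as two no-dose records: 25 − 2 = 23 (3.8 times).
- Entered as a 7-day interruption: 25 − 7 = 18 (3.0 times).

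**The other recording convention.** If all 17 planned off-days were entered as no-dose records and treated as interruptions, the formula gives 25 − 17 = 8, which is correct.

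**The case against.** The strongest objection is that the CRF page and its completion conventions are not in the documents. Section 13 bases all dosing calculations on that page and identifies interruptions only as entries with no dose, without separating planned from unplanned ones. If sites entered each planned off-day in that way, the row would be right. This cannot be excluded, and it stands as a limit: a reader might infer that the reported row is wrong for two of three cohorts, but the documents show only that the definition gives a wrong count on its plain reading. A definition whose correctness depends on an unstated data-entry habit still needs repair.

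The second objection is that little harm follows, and this also stands. Exposure is presented by regimen and dose, so the regimens remain labelled. The listing shows every administration, and the hematology line plots (SAP Section 15.4) also show treatment administration. Exposure duration, the number of cycles with at least 80% of planned dose, and the count of participants with a dose reduction do not use this formula. Membership of the DLT analysis set rests on cumulative dose and planned administrations (SAP Section 8.1), not on dosing days.

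The third objection is that only the one-cycle figure is firmly anchored, and only for a 28-day schedule. This is fair, and the longer and 21-day figures are offered as illustrations.

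**Conclusion.** The point holds as a definitional error of small consequence. For one fully compliant 28-day twice-weekly cycle the row would read 25 instead of 8, about three times too high, while the daily cohort would be correct. This assumes that planned off-days were not entered as no-dose records, which is the natural reading of SAP Section 13 and Protocol Section 6.4 but is not confirmed. The row is descriptive and feeds no endpoint, analysis set or dose decision.

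A reader might also infer that the SAP ignores regimen more widely, for example in the frequentist MTD suggestion of Section 15.1, where "All DLT data from the dose escalation will be included in a two-parameter logistic regression model" with no regimen term named. The documents do not support that inference. The same section uses nearly the same wording for the Bayesian model, which is fitted separately per regimen under the SMC analysis plan (Section 15.1) and Protocol Appendix 10. SAP Section 9 has analyses displayed by regimen, and the program code is in TLF shells that are not among the documents.

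**What to change.** In SAP Section 13, define number of dosing days as the number of distinct dates with a dose per administration above zero on the M3258 Administration Details page. This applies the section's existing definition of an administered dose. It gives 8 for the full 28-day twice-weekly cycle, 28 for the daily cycle, and 6 for the missed-dose example under either way of recording it. Because records with no dose drop out, it is also right if planned off-days were entered.

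The cost is one reworded definition and minor reprogramming. No new data are needed: the planned listing of administrations already requires the date and dose of each one.
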